2.3. Analysis Sets

2.3.1. Efficacy Analysis Set(s)

2.3.1.1. Intent-to-Treat Analysis Set

The intent-to-treat (ITT) analysis set is the primary analysis set for efficacy analysis. The ITT population will include all the subjects who were randomized and received at least 1 dose of treatment subsequent to randomization in the study. Subjects will be grouped according to the treatment arm (D/C/F/TAF or control) to which they were randomized.

2.3.1.2. Per Protocol Analysis Set

Since an analysis on the ITT population may not be conservative in a non-inferiority setting, an analysis based on the per protocol (PP) population will also be performed to investigate the impact of excluding subjects with major protocol violations and to evaluate the robustness of the primary analysis results. The PP population will include all subjects who:

- (1) are randomized into the study,
- (2) have received ≥ 1 dose of treatment in the study, and
- (3) without any major protocol deviation that is considered to potentially affect efficacy outcomes. Specific details are provided in Attachment 1.

2.3.2. Safety Analysis Set

The safety analysis (including all data collected up to 30-day follow-up visit) is also performed on the ITT analysis set.

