# 11.2. Subject Information

For all subjects who are randomly assigned to study drug and receive at least 1 dose of study drug descriptive statistics will be provided. Demographic and baseline disease characteristics will be summarized using standard descriptive methods (eg, sample size [n], mean, SD, median, minimum, maximum, frequency) as appropriate.

An intent-to-treat (ITT), per protocol (PP) and pharmacokinetic analysis population, will be defined:

- The ITT population will include all the subjects who were randomized and received ≥1 dose treatment in the study. Subjects will be grouped according to the treatment arm (D/C/F/TAF or control) to which they were randomized. The ITT analysis set is the primary analysis set for efficacy analysis. Efficacy data up to the last dose date of the randomized study treatment will be included.
  - The safety analysis (including all data collected up to the 30-day FU visit) is also performed on this analysis set.
- Since an analysis on the ITT population may not be conservative in a noninferiority setting, an analysis based on the PP population will also be performed to investigate the impact of excluding subjects with major protocol violations and to evaluate the robustness of the primary analysis results. The PP population will include all subjects who (1) are randomized into the study, (2) have received ≥1 dose of treatment in the study, and (3) without any major protocol deviation that is considered to potentially affect efficacy outcomes (eg, inadequate baseline resistance profile, use of concomitant medication interfering with antiviral efficacy, inadequate adherence to drug intake). Specific details will be provided in the Statistical Analysis Plan. The PP analysis set is the secondary analysis set for efficacy analysis.
- The pharmacokinetic analysis set will include all subjects who are randomized to the D/C/F/TAF arm (and the control arm, if applicable) and have received ≥1 dose of investigational treatment in the study, and for whom plasma concentration data of any analytes of interest are available.

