2. GENERAL ANALYSIS DEFINITIONS

2.1. Treatment Arms

Following notations for the treatment arms in the single arm treatment phase will be used:

- **Initial D/C/F/TAF Arm**: subjects who received D/C/F/TAF FDC treatment at baseline of the treatment phase
- Late Switch to D/C/F/TAF Arm: subjects who were on DRV/COBI FDC+ FTC/TDF FDC treatment and switched to D/C/F/TAF treatment during the single arm treatment phase

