5. SAFETY

For initial D/C/F/TAF, periods "Baseline to Week 48", "Week 48 to Week 96" and "Baseline to Week 96" will be presented in the tables. For the late switchers, periods "Baseline to Switch" and "Switch to Week 96" will be presented.

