5.1.2. Analysis Methods

A summary will be provided for the following treatment-emergent adverse events:

- any adverse events,
- serious adverse events,
- deaths due to AE,
- adverse events by toxicity grade (as well as AEs with toxicity grade at least 2 and AEs with toxicity grades 3 or 4),
- AEs at least possibly related to study medication,
- AEs for which the medication was temporarily/permanently stopped,
- serious adverse events that were at least possibly related to the medication.

Incidences of AEs for above mentioned analyses will also be presented by SOC and preferred term. A listing of all AEs will be provided. There will be no formal statistical testing.

Additionally, where applicable, the exposure adjusted incidence rates (EAIR) will be provided. EAIR is calculated as follows:

EAIR=n/\subsection to where n is the number of subjects with events, ti is subject's exposure time in patient-years Summary of events and incidence tabulations for individual adverse events will be provided for AEOI and also for ADRs.

AIDS defining illness based on WHO clinical staging will be tabulated.

The number and percentage of subjects who experienced fracture events (subgroups Fracture, possibly osteoporotic and Fracture other of the Bone AEOI for fractures) will be summarized by treatment group.

Selected safety endpoints will be explored by subgroups defined in section 2.4.2. Details for subgroup analyses of safety endpoints will be provided in the DPS.

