5.4.2. Analysis methods

Bone Biomarker:

Descriptive statistics for the actual values, change and percent changes from reference per time point will be presented for each bone biomarkers.

DXA scan:

Descriptive statistics for the actual values, change and percent changes from reference per time point will be presented for BMD parameters (including T- and Z-scores). Within-treatment arm comparison versus reference at Week 96 will be assessed using paired t-test.

The proportions of subjects with at least 3% change (decrease and increase separately) from reference in BMD will be presented at Week 96. Percent change from reference will also be tabulated based on thresholds; 5% and 7% (hip only).

BMD status will be tabulated (n, %) separately per time point, based on the T-score categories. Crosstabulations for the BMD status at Week 96 versus reference will be produced.

REFERENCES

- 2. Guidance for Industry. Antiretroviral Drugs Using Plasma HIV RNA Measurements Clinical Considerations for Accelerated and Traditional Approval. October 2002.

ATTACHMENTS

ATTACHMENT 1

PREDEFINED MAJOR PROTOCOL DEVIATIONS-based on the current list

The predefined major protocol deviations of this study are described in the Protocol Deviation Criteria document. The deviations that are considered to have an (possible) impact on efficacy are a subset of the predefined major protocol deviations and are indicated with 'Yes' below (column 'Exclude from Per Protocol Analysis') and if such deviations are reported for a subject, the subject will be excluded from the PP analysis.

In addition to the below table, the following subjects will also be excluded from the per-protocol analysis set:

- Subjects with treatment adherence based on drug accountability derivation ii for the active ARVs (worst D/C/F/TAF adherence between baseline to switch and switch to Week 96 for the Initial D/C/F/TAF treatment group and worst adherence across DRV/COBI FTC/TDF, and D/C/F/TAF for the Late Switch to D/C/F/TAF treatment group) <65%. For the purpose of the per-protocol analysis set only, subjects with missing treatment adherence will be assumed to be above 65%.

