- Subjects with no post-baseline viral load measurement (e.g., discontinued within 2 weeks).

29

Sequence No.	Description	Protocol Deviation coded term (DVDECOD)	Exclude from PP	
1	Screening plasma HIV-1 RNA level < 1,000 copies/mL	Entered but did not satisfy criteria	Yes	
2	The subject uses disallowed concomitant therapy specified in the protocol.	Entered but did not satisfy criteria	Yes	
3	The subject has any known allergies to the excipients of the D/C/F/TAF, or DRV/COBI, or TDF/FTC tablets, but the subject was randomized	Entered but did not satisfy criteria	Yes	
4	The dose of Investigational treatment arm (D/C/F/TAF tablet) or the active control arm was temporarily not according to protocol for more than 4 consecutive weeks.	Received wrong treatment or incorrect dose (missed dose or extra dose)	Based on >4 weeks period.	
5	The intake of Investigational treatment arm (D/C/F/TAF tablet) or the active control arm was interrupted for toxicity reasons for more than 4 consecutive weeks.	Received wrong treatment or incorrect dose (missed dose or extra dose)	In that case classified as major and excluded from PP	
6	The intake of Investigational treatment arm (D/C/F/TAF tablet) or the active control arm was interrupted for non - toxicity reasons for more than 4 consecutive weeks, or cumulatively for more than 8 weeks.	Received wrong treatment or incorrect dose (missed dose or extra dose		
7	The subject takes disallowed medication as defined per protocol.	Received a disallowed concomitant treatment	Yes (adjudication based on drug/class and duration).	
8	Subjects not showing genotypic susceptibility to DRV, FTC, TFV	Entered but did not satisfy criteria	Yes	
9	The subject missed two or more consecutive planned visits in the trial	Other	Yes	

Approved, Date: 25 April 2018

Sequence No.	Description	Protocol Deviation coded term (DVDECOD)	Exclude from PP
10	Misallocation of Medkits was observed during Dosage and administration of study drug and subject treated differently than what they were randomized to for more than 4 weeks	Other	Yes
11	After achieving confirmed (consecutive) HIV-1 RNA <50 copies/mL prior to Week 96 and scheduled Week 96 achieving HIV-1 RNA ≥ 50 copies/mL or >1log ₁₀ increase in HIV-1 RNA from the nadir at scheduled Week 96, but no retest in Week 96 window (90-102 weeks)	Other	Yes
12	Subject missed the Week 96 visit.	Other	Yes

31

ATTACHMENT 2

Adverse Events of Interest: List of Preferred Terms

AEOI	AEDECOD (MedDRA v19.1)

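### Safety and bone data are grouped only as randomised, so the plan has no as-treated summary for a subject who took the other regimen's kits for more than 4 weeks

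*SAP*

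**What the plan says.** SAP 2.3.2 states that the safety analysis "is also performed on the ITT analysis set". The rule for that set is in SAP 2.3.1.1: "Subjects will be grouped according to the treatment arm (D/C/F/TAF or control) to which they were randomized". Protocol 11.2 takes the same position: "The safety analysis (including all data collected up to the 30-day FU visit) is also performed on this analysis set". SAP 2.3.3 repeats the randomised grouping for the bone investigation set.

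SAP Attachment 1, deviation 10, describes misallocation of medication kits with the "subject treated differently than what they were randomized to for more than 4 weeks". The attachment gives the consequence of the deviations it marks for exclusion: "if such deviations are reported for a subject, the subject will be excluded from the PP analysis". SAP 3.5 adds that major deviations are tabulated and listed by arm. Neither document gives a rule for the safety or bone data of such a subject.

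SAP 2.1 labels the reporting groups for the single-arm phase and describes the Initial D/C/F/TAF arm as "subjects who received D/C/F/TAF FDC treatment at baseline of the treatment phase". SAP 5 presents safety for the initial and late-switch groups, split by period.

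**The concern.** Safety data are normally read by the treatment that was taken. The two arms differ in the tenofovir prodrug, and protocol 3.2 says the choice of control permits a direct safety comparison of TAF with TDF. Protocol 1.7 names kidney and bone as the main nonclinical toxicities of TAF, and protocol 3.3 reports roughly 90% lower tenofovir exposure with the combination tablet than with the TDF regimen. A subject randomised to one arm but supplied with the other arm's active tablets for months contributes creatinine, urinary markers, bone density and adverse events that belong to the other regimen.

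The plan treats such a deviation as serious enough to remove the subject from per-protocol efficacy, yet leaves the safety data where they are. The subject's time at risk also stays in the randomised arm, so both numerator and denominator of the exposure-adjusted incidence rates in SAP 5.1.2 are affected.

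**Working it through.** The point rests on definitions, and the plan states no figure to reproduce. The arithmetic below only gives scale.

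**Reading the sections together**

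1. Safety set = ITT set (SAP 2.3.2). ITT set = grouped as randomised (SAP 2.3.1.1). So safety is grouped as randomised.
2. The bone set is grouped as randomised in its own right (SAP 2.3.3). A change to SAP 2.3.2 alone would not reach it.
3. Deviation 10 leads to per-protocol exclusion. The per-protocol set is an efficacy set (SAP 2.3.1.2), so the exclusion does nothing to safety.
4. After the switch every subject is to receive D/C/F/TAF, so the gap concerns the double-blind and extended double-blind periods.
5. The SAP already separates safety from efficacy attribution in one place. For the extra visit 3 to 7 weeks after unblinding, SAP 2.2.1 assigns safety data to D/C/F/TAF and efficacy data to the control regimen. The same idea is not carried over to misallocation.

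**Size for one subject**

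Inputs: 335 planned per arm (SAP 1.2) and a minimum of 85 per arm in the bone substudy (SAP 1.4).

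- Main study: 1/335 = 0.30 percentage points of one arm's incidence.
- Bone substudy: 1/85 = 1.18, about 1.2 percentage points, for a proportion such as subjects passing a bone density threshold.

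These are upper figures for one arm and apply when the subject has the event. If a subject with the event were moved wholly to the other arm, both incidences would change, and the difference could move by up to about 2 × 0.30 = 0.60 points. A subject without the event matters far less: removing one from an arm with an assumed 10% incidence shifts it by 0.10/334 = 0.03 points.

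**Size for several subjects**

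The number misallocated is not in the documents, so it is assumed. Let a fraction m of each arm take the other regimen throughout, unrelated to outcome, with true event rates pT and pC. The expected observed rates are (1 − m)pT + m·pC and (1 − m)pC + m·pT. Their difference is (1 − 2m)(pT − pC).

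With illustrative rates of 10% and 15% (true difference −5.0 points):

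| Misallocated per arm (of 335) | m | 1 − 2m | Expected observed difference |
|---|---|---|---|
| 1 | 0.30% | 0.994 | −4.97 |
| 3 | 0.90% | 0.982 | −4.91 |
| 7 | 2.09% | 0.958 | −4.79 |
| 17 | 5.07% | 0.899 | −4.49 |

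Misallocation for only part of the period dilutes less.

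**Why the rule must follow time on treatment**

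Deviation 10 is met once misallocation exceeds 4 weeks. A subject misallocated for 5 of 48 weeks spent 5/48 = 10.4% of the time on the wrong regimen and 89.6% on the randomised one. Moving that subject wholly to the other arm would create a larger misattribution than it removes.

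**The case against.** The strongest reply is that this is a descriptive Week 96 analysis in which little depends on the grouping. For adverse events the SAP says "There will be no formal statistical testing". The renal and bone density tests it plans compare each arm with its own reference. The formal between-arm safety tests in protocol 11.6 are at Week 48 (for bone, Weeks 24 and 48), and this SAP does not cover that analysis. All of this stands: no between-arm safety test in this plan is affected.

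Cases also stay visible, because major deviations and all adverse events are listed. That stands too, but a reader would have to match the listings by hand, and no summary would show the effect.

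The protocol itself specifies the ITT set for safety. SAP 1.5 describes unblinding as past, and the SAP is dated 25 April 2018. Replacing the safety set now would be a departure made after unblinding and could disagree with the Week 48 tables. This argues for adding summaries and against redefining the set.

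A reader might infer more than the documents support:

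- **That SAP 2.1 contradicts SAP 2.3.1.1** because it speaks of treatment received. SAP 2.1 is introduced as notation for the single-arm phase, does not mention misallocation, and for the initial arm looks only at baseline. It reads most naturally as shorthand for the randomised arms. Even taken literally, it would not catch a wrong kit dispensed later.
- **That the bias is always towards no difference.** That holds only in expectation and only if misallocation is unrelated to outcome. With one or two subjects the realised shift can go either way.
- **That misallocation happened or was expected.** A predefined deviation category shows only that it was considered possible.

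**Conclusion.** The gap is real and small. Under the stated rules, a misallocated subject's adverse events, renal and bone data and exposure time before the switch are reported under a regimen that was not being taken, and nothing in the plan shows the result by treatment received. The size is at most about 0.3 points of an arm's incidence per subject in the main study and about 1.2 points in the bone substudy, assuming the planned 335 and 85 per arm. It would be most noticeable for rare events, where one case can be seen in a table. Dilution of the contrast is an expectation that depends on misallocation being unrelated to outcome.

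This is a cheap improvement. It does not touch the primary efficacy conclusion, and it has no effect if no misallocation occurred.

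**What to change.** Keep the randomised grouping for efficacy and for the safety tables that the protocol specifies. Then:

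1. Add as-treated safety summaries in which a misallocated subject's adverse events and exposure time are attributed to the regimen being taken at the time.
2. For summaries with one value per subject, such as renal or bone density change, group the subject by the regimen taken for most of the period summarised.
3. Apply the same rule to the bone set in SAP 2.3.3.
4. List the adverse events of misallocated subjects, with the dates on each regimen.
5. Record these summaries as an addition to protocol 11.2.
6. State in SAP 2.1 that the group labels are notation for the randomised arms.

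The cost is a few lines of SAP text and a few extra tables. The tables are needed only if a misallocation occurred; otherwise the output is unchanged.

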2.3.3. Bone Investigation Sub-study Analysis Set

The bone investigation sub-study (BIS) analysis set will include all subjects who are randomized and have received ≥1 dose of treatment in the study, and have at least one post-reference value either in biomarker or in BMD data. Subjects will be grouped according to the treatment arm (D/C/F/TAF or control) to which they were randomized.

2.4. Definition of Subgroups

2.4.1. Subgroups for Efficacy Analyses

- Adherence based on D/C/F/TAF (i.e., worst D/C/F/TAF adherence from baseline to switch and switch to week 96 for the Initial D/C/F/TAF group, and from switch to week 96 for the Late Switch to D/C/F/TAF group) on drug accountability for both derivations (>95%: adherent, ≤95%: non-adherent, missing/unknown)
- Re-classified (see section 2.5) viral load stratification factor ($\leq 100,000, \geq 100,000$ copies/mL)
- Re-classified (see section 2.5) CD4+ count:
 - \circ < 200, \geq 200 cells/mm³[200 \leq x<350, 350 \leq x \leq 500, >500 cells/mm³]
- Combination of re-classified (see section 2.5) stratification factors:
 - o Viral load < 100,000 copies/mL and CD4+ < 200 cells/ mm³
 - o Viral load $\leq 100,000$ copies/mL and CD4+ ≥ 200 cells/ mm³
 - o Viral load > 100,000 copies/mL and CD4+ < 200 cells/ mm³
 - O Viral load > 100,000 copies/mL and CD4+ ≥ 200 cells/ mm³
- Race (American Indian or Alaska Native, Asian, Black or African American, White, Native Hawaiian or other Pacific Islander, Other, Non Black or African American)
- Ethnicity (Hispanic or Latino, Not Hispanic or Latino)
- Gender (Male, Female)
- Age group:
 - \circ \leq 50, >50 years
- Region (Europe, North America)
- WHO Clinical Staging of HIV/AIDS
- HIV-1 subtype (B, non-B)
- Any PI RAMs (primary + secondary) (0-3, 4-6, 7-9, >=10)
- Presence (Yes/No) of one or more:
 - o primary and/or DRV RAMs,
 - o NRTI RAMs,
 - o NNRTI RAMs,
 - o M184V/I

Subgroup analyses will be performed on the ITT analysis set.

2.4.2. Subgroups for Safety Analyses

- Age group:
 - \circ \leq 50, >50 years
- Re-classified (see section 2.5) viral load stratification factor (≤ 100,000, > 100,000 copies/mL)
- Re-classified (see section 2.5) CD4+ count ($< 200, \ge 200 \text{ cells/mm}^3$)
- Combination of re-classified (see section 2.5) stratification factors:
 - o Viral load $\leq 100,000$ copies/mL and CD4+ < 200 cells/ mm³

- Viral load \leq 100,000 copies/mL and CD4+ \geq 200 cells/ mm³
- \circ Viral load > 100,000 copies/mL and CD4+ < 200 cells/ mm³
- \circ Viral load > 100,000 copies/mL and CD4+ \geq 200 cells/ mm³
- Race (American Indian or Alaska Native, Asian, Black or African American, White, Native Hawaiian or other Pacific Islander, Other, Non Black or African American)
- Ethnicity (Hispanic or Latino, Not Hispanic or Latino)
- Gender (Male, Female)
- Region (Europe, North America)
- WHO Clinical Staging of HIV/AIDS

Subgroups for Bone Investigation Analyses:

- Race (American Indian or Alaska Native, Asian, Black or African American, White, Native Hawaiian or other Pacific Islander, Other, Non Black or African American)
- Gender (Male, Female)
- Baseline BMI:
 - \circ Underweight (< 18.5 kg/m²)
 - o Normal range $(18.5 24.99 \text{ kg/m}^2)$
 - o Overweight $(25.0 29.99 \text{ kg/m}^2)$
 - \circ Obese ($\geq 30.0 \text{ kg/m}^2$)
- Age group (\leq 50, >50 years)
- Current smoking status (Y/N)

2.5. Re-classification of Stratification Factors for Purpose of Analysis

For the purpose of analysis the stratification factors (HIV-1 RNA [$\leq 100,000, > 100,000$ copies/mL] and CD4+ count [($< 200, \geq 200$ cells/mm³]) will be re-classified based on the baseline values from the laboratory data. If the baseline data are missing, then the laboratory data at screening will be used. If the laboratory data at screening are missing, then the data from the IVRS/IWRS will be used.

The re-classified stratification factors will be used for analysis. Listings showing the discrepancies between the strata entered at randomization (IVRS/IWRS) and actual screening laboratory data will be presented.

2.6. Reference

For Initial D/C/F/TAF group, reference is the comparative treatment phase baseline as in Week 48 analysis. For the Late Switch group, the references are as follows:

- 1. Comparative treatment phase baseline (for efficacy this reference will be used for periods before and after the switch; for safety this reference will be used for periods before the switch).
- 2. Last value prior to the switch will be used as a reference for periods after the switch for both efficacy and safety; for DXA scan, data up to (and including) 28 days after the switch to open label D/C/F/TAF can be used as reference.

3. SUBJECT INFORMATION

3.1. Demographics and Baseline Characteristics

These parameters will not be included in this analysis, because no new subjects were recruited since the Week 48 analysis.

3.2. Disposition Information

A tabulation of the total number (with percentages) of subjects screened, randomized and not treated and randomized and treated will be provided.

Tabulation per treatment arm of the number of subjects who have completed the treatment/single arm phase, who are ongoing, and who have discontinued the trial with the reason for discontinuation will be provided. For the Initial D/C/F/TAF group, the tabulation will be presented by time period as follows; baseline to Week 48, Week 48 to Week 96 and overall from baseline to Week 96. For the Late Switch group, the tabulation will be presented by time period as follows; baseline to Week 48, Week 48 to the switch, from the switch to Week 96, and overall from baseline to Week 96.

A Kaplan-Meier graph for the time to Study Discontinuation (any reason) will be included.

